**C. Indicate the stage or type of the investigation**

- ◆ Stage I
- Stage II
- Nonclinical study
- Other

**D. Describe oversight procedures in place for departments, clinical units, or operating rooms where devices are used which provide for independent monitoring of the storage and dispensing of devices, and for required record-keeping.**

The patients will use their own smartphone to download and use the BNN app. Therefore, there is no need to monitor the devices. They will be provided directions on how to delete the app at anytime.

**E. Does this research involve an investigational in-vitro diagnostic device (IVD)?**

No

**CONFIDENTIALITY AND PRIVACY**

**15. Confidentiality and Privacy**

**A. Describe where research data will be stored. Check all that apply.**

- ◆ On a secure server at UNMC, CHMC, Nebraska Medicine, and/or UNO (including REDCap)
- ◆ On a secure cloud server - Specify the secured cloud serve: OneDrive

On a firewall protected database accessible through the internet - Specify who has administrative responsibility for maintenance of the server:

On an encrypted, password protected local hard drive  
On an encrypted, password protected portable computer  
On an encrypted, password protected flash drive  
◆ In hard copy  
Other

**a. Please provide justification for use of hard copies**

BHPs have the option of providing face to face or virtual visits with the patients. In the event that a patient presents face to face then a hard copy consent would be used.

**b. Will hard copies will be transported from one site to another, on or off campus?**

Yes

**c. Describe how they will be secured during transport**

locked briefcase.

**B. Will any of the following subject identifiers be recorded (at any time) in association with the research data?**

Yes

**1) Indicate the subject identifiers that will be recorded. Check all that apply.**

- ◆ Name
- ◆ DATES (e.g. date of study visit, date of sample collection, birth, admission, discharge)
- ◆ Postal address information: street address, city, county, precinct, ZIP code
- ◆ Telephone numbers
- Fax numbers
- ◆ Electronic mail addresses
- Social Security numbers
- Medical Record numbers
- Health plan beneficiary numbers
- Account numbers
- Certificate/license numbers
- Vehicle identifiers and serial numbers, including license plate numbers
- Device identifiers and serial numbers
- Web Universal Resource Locators (URLs) Internet Protocol (IP) address numbers
- Biometric identifiers, including finger and voice print
- Full face photographic images [and any comparable images]

No Identifier

**2) Will a unique subject identifying number (e.g., S1, S2, S3), characteristic or code be used to link data to any of the identifiers listed above?**

Yes

**a. Where will the key (that links the unique subject identification code to the subject's name or other identifier) be stored?**

The BHP's will keep a list of patient names and study IDs electronically in their own project folder that can be accessible only by them using the password.

Participants who contact the research team through clinical trial registry will only receive emails or telephone calls from UNMC researchers/investigators associated with this IRB for the purposes of discussing potential participation with the potential recruitment. A log with unique identifiers associated with the patients subject identifiers will only be accessible by members of the UNMC researchers/investigators associated with this IRB

[name] will keep the list of BHP names, Clinical Staff, Providers and Administration and study IDs electronically in her own project folder which only she will be able to access. Identifiable information which will be collected from the BHPs, Clinical Staff, Providers and Administration and include, name, gender, years of employment, number of years at the clinic, and clinic location.

**b. Does the code number include the subject's initials or other subject identifier as part of the code?**

No

**3) What is the justification for recording the specific subject identifiers listed above?**

**Check all that apply.**

Schedule appointments

Collect continuous clinical information from the medical records

♦ Follow-up with subjects

Link stored tissue with subject identification for it to be withdrawn in the future if requested

♦ Compensation

Other. Explain.

**4) How long will the subject identifiers be maintained in association with the research data?**

Once the study data has been collected and analyzed the subject identifiers will be

destroyed according to UNMC IRB policy and procedures (7 years following completion of the study).

**5) How will all of the identifiable research data be destroyed (e.g., all identifiers stripped from the data and destroyed, hard copies shredded etc) when the identifiable data is no longer required?**

All identifiable research data will be destroyed once the study data has been collected and analyzed. The subject identifiers will be destroyed according to UNMC IRB policy and procedures. The PI will work with UNMC IT to ensure all data is stripped and destroyed according to UNMC IRB policy guidelines. Study materials that do not contain patient identifiers will be retained for the designated 7-year timeframe. After which the PI will work with UNMC IT to ensure all data is stripped and destroyed according to UNMC IRB policy guidelines. Audio files from focus groups will be deleted per UNO IT policy after data analysis is complete.

**C. Will research data that contain subject identifiers be disclosed to: Other investigators at UNMC, NM, UNO or CHMC who are not listed in Section I of this application?**

No

**2. Investigators outside of UNMC, NM, UNO or CHMC?**

No

**3. Will research data that contain subject identifiers be disclosed to any commercial sponsor or contract research organization (CRO), or to any other external organization or entity (e.g., NCI cooperative groups)?**

No

**D. What provisions will be in place to protect the subject's privacy? Check all that apply.**

- ◆ Ensuring that only personnel listed on the IRB application Section I.3(A-E) are present during the consent process.
- ◆ Ensuring that the fewest number of individuals possible are aware of the subject's participation in the research.
- ◆ Ensuring that the research activities are performed in as private of a place as possible.

Other. Explain.

**E. Does this research involve data banking at UNMC, NM, UNO or CHMC, or by an outside organization (e.g. NCI Cooperative Group, pharmaceutical company) for future**

**research that is not related to this study?**

No

## **RISK/BENEFIT ASSESSMENT**

### **16. Potential Risks**

**What are the potential risks associated with each research procedure, intervention, evaluation and/or test? If data are available, estimate the probability that a given harm may occur and its potential reversibility.**

We anticipate the minimal risk associated with the use of BBN. BBN has been studied extensively and found to produce no known harms to the patients. However, it is possible that the use of some features of the app may trigger some negative psychological response. In case, the patient experiences any negative consequences from using the app, the patient will be directed to contact the clinic BHP.

The potential risks to subjects associated with the study interactions are deemed to be minimal. We do not anticipate any physical risks. The psychological, social, cultural, financial, and legal risks are breach of confidentiality which may result in negative psychological experience. Risks to privacy and/or confidentiality are minimal as the focus group participants will not be asked to provide personal health information and we will adhere to IRB privacy and confidentiality standards for each aim of the study. We will however review all risks and ensure informed consent is completed with each participant prior to the start of the study. In order to protect patient privacy, we will use unique study IDs to the patients. The BHPs, who have ethical access to the participants, will keep the spreadsheet that contains the participants name and medical record number as well as the study ID.

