## **CHARACTERISTICS OF THE SUBJECT POPULATION**

### **4. Accrual**

**A. Is this study conducted solely at sites under the oversight of the UNMC IRB (e.g. UNMC, Nebraska Medicine, CHMC, UNO)?**

Yes

**1. How many subjects will need to be consented (per group, as applicable) in order to achieve the scientific objectives of the research?**

Aim 1: Total 14 - 10 patients and 4 behavioral health providers

Aim 2: Total 45 - Patients (15), BHPs (10), Clinical staff, providers and administration (20)

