**2. What is the statistical or other justification for the total number of subjects described above?**

Because of the pilot nature of the study, it is not anticipated that quantitative results will achieve statistical significance. The data will primarily serve to demonstrate feasibility of our approach and success recruitment for a larger clinical trial. We aim for the number indicated in Section II 4 A 1, based on our ability to recruit patients at the clinic during the pilot funding period.

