study is voluntary and does not affect their care or access to BBN. The BHP will also assist the patient with the QR code, if necessary, but it is anticipated that participants will interact with this link after the session has ended, which will reduce both patient and provider burden by minimizing disruption to services. The BHP will be trained to problem solve QR code usage with the patient to ensure they can access the link before leaving. The Redcap survey will begin with a modified consent form (it is modified in accordance with the prior waiver of written consent we received previously where participant will confirm the consent electronically). If participants agree to participate in the study, they will then complete a series of questionnaires. All questionnaires are standard in survey research and do not contain any items that identify risk or result in significant distress. They are listed under Research Assessment below. The measures do contain an assessment of stressful event exposure, but prior studies indicate that such measures do not significantly increase participant distress and more frequently report research studies involving such measure as a positive experience overall (Jaffe et al., 2015). Further, the consent procedures will explicitly suggest that participants complete the survey in a private setting and inform the participants that the study will contain questions about stressful life experiences. Additionally, participants will be afforded the opportunity to complete the study in a private setting at the clinic, though we anticipate some participants may choose to complete the survey after. They will be advised that they should complete the consent form and survey within two days of their appointment. At the end of the survey, they will be given information that they should reach out to their BHP if they would like to further discuss any symptoms or topics discussed during the assessment and that they may contact the research team with any questions about the study. The Redcap will also automatically redirect to a separate survey where participants can provide contact information for compensation and follow-up phone surveys (see Follow-up Phone surveys below). Participants will be able to provide contact information for compensation and still decline participation in follow-up phone surveys. Participants will also be able to indicate a preference for completing follow-up surveys electronically and receiving the link via email or text or completing the survey over the phone. They will be asked to provide the contact information corresponding with their preference.

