With regard to data safety issues, Health Information Technology Solutions (HITS), the company that manages BBN on servers at the Medical University of South Carolina (MUSC) utilizes secure, confidential, user-friendly digital spaces. These are an n-tier architecture with responsive multichannel capability such that participating clinical staff, which we refer to as advocates, can access the components via a HIPAA compliant website or mobile application on smartphone or tablet (IOS, Android, Windows, etc.). HITS has proven software development architecture that allows for seamless delivery of content in a consistent, customized experience regardless of device, media form, or operating system. Respondent confidentiality will be masked by the use of participant ID numbers rather than personal information. Moreover, all data will be stored using resources located in the HITS facilities in the School of Nursing at Medical University of South Carolina (MUSC) until de-identification is complete. Electronic data will be stored on secure, password-protected computers/servers on site. De-identified use data will be transferred to investigators at UNL via secure, cloud-base storage. These data will be linked with interview data via cross-linking of app initiation dates and times, which will prevent even HITS staff from ever having access to identifiable information of users. The interview data and combined interview data will be stored at UNL facilities through secure servers at the Rural Drug Addiction Research Center (RDAR). When processed data are ready for data analyses, those analyses will be performed through protected storage at UNL.

**C. Describe the auditing plan for research conducted. Identify who will conduct the audits and specify the audit frequency.**

Either [name] or [name] will audit the study at the 6-month point.

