**D. Describe the specific subject withdrawal criteria.**

Participants will be withdrawn if he/she voluntarily withdraws his or her consent to participate in a study at any time for any reason. Participants will also be withdrawn if any time they are experiencing any indication of suicidality and/or experiencing difficulty, either physically or mentally, with the study. Should this occur these events will follow the current

standard of care within their respective treatment facility.

**E. Describe the stopping rules for the research (e.g., the specific criteria for halting or early termination of the study).**

If for some reason the participant becomes upset during the interview, the qualitative researcher will bring the interview to the end, thank the participant for his/her participation and be available afterward to discuss any concerns participants may have. If 2 or more subjects become upset and require withdrawal from the trial, the trial will be halted.

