**F. Describe plans and resources available to promptly address any subject injury.**

This research involves mobile app use and survey/interview-based primary data collection in a safe indoor environment. There is no intervention or any other physical or medical procedure that may pose a risk of a research-related injury to the subjects. However, if any subject expresses distress related to questions asked or discussed, they will be referred to their primary care provider for follow-up, either through self-referral or referral made by an investigator.

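### The protocol names an app-triggered negative psychological response as a risk, but no listed follow-up instrument is described as asking whether BBN caused one, and nobody is named to review Aim 2 follow-up answers for safety.

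*Combined protocol and SAP*

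**What the plan says.** **Risk and route.** Section II, 16 says that "it is possible that the use of some features of the app may trigger some negative psychological response" and that, if the patient has negative consequences from the app, "the patient will be directed to contact the clinic BHP". It does not say that the event is recorded or passed to the study team.

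**Follow-up.** Under 12.B, surveys are due 2 and 6 weeks after baseline, online or by phone, and a patient may decline them. PHQ-9, GAD-7, PROMIS Depression 8a, PCL-5 and the Pittsburgh Sleep Quality Index are repeated at follow-up. A usability questionnaire (MAUQ) and the User Burden Scale come later, and patients are invited to an interview. The Aim 2 baseline text describes the survey thus: "All questionnaires are standard in survey research and do not contain any items that identify risk or result in significant distress". The app itself records only utilization. BHP visits continue as standard care dictates.

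**Monitoring.** 18.A describes watching for distress only in participants who come through the trial registry, and says that this route serves Aim 1. 18.B asks who performs ongoing safety analysis and how often. The answer begins "With regard to data safety issues, Health Information Technology Solutions (HITS), the company that manages BBN on servers" and stays with data security and linkage. 18.C plans an audit at 6 months.

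**Withdrawal and halting.** 18.D withdraws a patient at any time for suicidality or for physical or mental difficulty with the study. 18.E opens "If for some reason the participant becomes upset during the interview, the qualitative researcher will bring the interview to the end", and then halts the trial once two or more subjects are upset and need to be withdrawn.

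**The concern.** BBN includes written exposure and expressive writing for PTSD, used at the patient's own pace by people with trauma-related symptoms. A negative reaction is the one app-specific harm that the protocol foresees, and it would most likely arise between visits. A patient who is upset by a writing exercise in week 1 and stops would appear in the usage log as someone who stopped. The log cannot tell distress from lost interest.

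At stake is what the pilot can say at its end. It is meant to expose procedural problems before a full-scale study. A statement that no app-related harm was seen would be carried into that study's design and risk section, although the patients had not been asked directly. An acceptability finding that matters in trauma patients could be lost as well.

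**Working it through.** The plan has no safety figure to reproduce. The check sets the sections side by side and then shows how far a report of no harm depends on how completely cases are found.

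**1. Could each stated source identify an app-triggered reaction in an Aim 2 patient?**

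| Source | What it gives | What it lacks |
|---|---|---|
| PHQ-9, GAD-7, PROMIS 8a, PCL-5, sleep index, weeks 2 and 6 | Symptom level during app use | Attribution to BBN; a named reader |
| User Burden Scale, MAUQ | Burden and usability | Not described as asking about an adverse reaction |
| Usage log | Last use, number of logins, access per component | The reason for stopping |
| Patient interview, at or after week 6 | Acceptability, components, strengths and weaknesses | Late; by invitation; no harm question described |
| BHP visits | Clinical contact | No study schedule, no harm enquiry, no stated report to the team |
| Patient contacts the BHP | The stated route | Depends on the patient; no stated report to the team |

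The interview timing combines 12.B (a later date) with section 23 (possibly the second follow-up call). This table uses the protocol's descriptions of the instruments. Their individual items are not in the documents.

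**2. Could worsening scores stand in for the missing question?** 12.C selects neither randomization nor a placebo or non-treatment arm. A worse score may reflect BBN, the underlying condition or ordinary fluctuation, and nothing in the design separates these. The protocol also names no person, frequency or threshold for reviewing scores for safety.

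**3. Are visits a dependable substitute?** The protocol's own background (section 3) says that most patients in integrated primary care attend no more than two sessions.

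**4. How much does completeness matter with 15 patients?** Inputs:
- n = 15 Aim 2 patients (section 4, Accrual).
- p = true proportion with an app-triggered negative response. Not in the documents, so assumed.
- s = share of those cases that reach the study team. Not in the documents, so assumed.

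Treating patients as independent, the chance that the pilot records no case is (1 − p × s)^15.

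| p | s = 1 | s = 0.5 | s = 0.25 |
|---|---|---|---|
| 5% | 0.463 | 0.684 | 0.828 |
| 10% | 0.206 | 0.463 | 0.684 |
| 20% | 0.035 | 0.206 | 0.463 |
| 30% | 0.005 | 0.087 | 0.311 |

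Example: p = 20% and s = 0.5 gives (1 − 0.10)^15 = 0.206.

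Even with every case found, 0 of 15 leaves a one-sided 95% upper limit of 1 − 0.05^(1/15) = 18.1%. If only half of cases are found, that limit applies to p × s, and the limit on p is 18.1% / 0.5 = 36.2%.

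**The case against.** The strongest reply is that distress is measured. Four scales of depression, anxiety and PTSD symptoms are repeated during app use, and app-specific feedback comes from the User Burden Scale and the interviews. Patients are already under BHP care, and the baseline survey ends by telling them to contact their BHP about symptoms. Because the 2-week survey is described as identical to baseline, that prompt may well recur. The study is classed as minimal risk, the app is free and public, and the sample size section says that "it is not anticipated that quantitative results will achieve statistical significance". All of this stands, and it limits the point to attribution, review and recording.

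Four stronger readings are tempting, and the documents do not support them:

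- **That nothing in follow-up bears on distress.** The repeated scales contradict this. The sentence about items that identify risk belongs to an argument that the questionnaires themselves do not upset patients. It is not a statement of safety policy.
- **That the halting rule applies only to the interview.** Only the opening of 18.E is set there. The sentence on two or more subjects names no setting, and 18.D applies at any time. The scope is unclear, and no route from app use to the rule is described.
- **That sections 16 and 18.F contradict each other on whom to contact.** Section 16 concerns consequences of using the app. 18.F says that "if any subject expresses distress related to questions asked or discussed, they will be referred to their primary care provider for follow-up". The triggers differ.
- **That one can calculate how often the halting rule would be missed.** It counts subjects who are upset and also need withdrawal, which is narrower than any unwanted response. The documents give a rate for neither.

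**Conclusion.** The point holds as an ascertainment gap. The protocol names a risk, measures symptoms that might reflect it, and leaves out both a direct question linking the two and a person to look at the answers. Followed as written, harm during app use can go unrecorded, and a report of no harm would carry little information. That is not evidence that BBN causes harm.

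On size, two scheduled surveys per patient exist, and neither is described as containing such a question. The probabilities rest on assumed values of p and s and on independence between patients. What does not depend on the exact values is that, for any given rate, a lower share of cases found makes a report of no harm more likely. For a minimal-risk pilot this should be corrected, and existing contacts suffice to do so.

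**What to change.** 1. Add one fixed item to the 2- and 6-week surveys, worded the same online and by phone. It asks whether using BBN made the patient feel worse or upset, which section was involved, and whether use stopped.
2. In 18.B, name an existing team member who reads these answers and the follow-up symptom scores as they arrive. Extend 18.A to Aim 2 patients.
3. Tabulate the count as a safety and acceptability outcome, with the number of patients who answered the item as denominator. Follow-up may be declined, so this can be below 15.
4. Reconcile 18.D and 18.E with section 16, 18.A, 18.B and the Aim 2 baseline text on two matters: whether the rules cover the whole period of app use, and how cases reach the study team. The clinical response and any stopping rule are for the investigators to set.

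**Cost.** At most 2 × 15 = 30 extra responses, an alert in REDCap and some rewording. Burden rises slightly, and some complaints will be non-specific. More events will come to the team's attention in a sample of 15, so the investigators should settle the scope of 18.D and 18.E before the item goes live. The item will not reach patients who decline follow-up, and it asks at two time points only.
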